### 7.2. Participant Withdrawal from the Trial

Each participant is free to withdraw from the trial or discontinue from IMP at any time, without prejudice to their continued care. Participants must be withdrawn from the trial if any of the following events occur:

- Participant withdraws consent or requests discontinuation from the IMP or withdrawal from the trial for any reason.
- Participant develops an illness that would interfere with his/her continued participation.
- Participant is noncompliant with the trial procedures and assessments or administration of IMPs in the opinion of the Investigator.
- Participant takes prohibited concomitant medications chronically.

- A female participant has a confirmation of pregnancy during the trial from a positive pregnancy test.
- The Sponsor requests withdrawal of the participant.
- Participant experiences an adverse event or other medical condition indicating to the Investigator that continued participation is not in the best interest of the participant.
- Any participant who demonstrates suicidal ideation and/or any suicidal behavior at any point during the trial should be withdrawn from the trial and discontinued from trial treatment.

Participants should be treated with standard of care after withdrawal from or termination of the trial as appropriate.

Investigators should attempt to obtain information on participants in the case of withdrawal from the trial or discontinuation from IMP. Results of any evaluations and observations, together with a narrative describing the reason(s) for withdrawal from the trial or discontinuation from IMP, must be recorded in the source documents. The CRF must document the primary reason for withdrawal from the trial or discontinuation from IMP.

See Section [7.3](#) for information regarding how the trial will define and address lost to follow-up participants to help limit the amount and impact of missing data.

If the reason for withdrawal from the trial or discontinuation from IMP is an adverse event and/or clinically significant abnormal laboratory test result, monitoring will be continued as applicable (eg, until the event has resolved or stabilized, until the participant is referred to the care of a health care professional, or until a determination of a cause unrelated to the IMP [and/or PFS] or trial procedure is made). The specific event or test result (including repeated test results, as applicable) must be recorded both on the source documentation and in the CRF; both the adverse events page and the relevant page of the CRF will be completed at that time.

The Investigator must inform the Trial Leader as soon as possible of each participant who is being considered for withdrawal due to adverse events. Additional reports must be provided when requested.

If a participant is withdrawn from the trial for multiple reasons that also include adverse events, the relevant page of the CRF should indicate that the withdrawal was related to an adverse event. An exception to this requirement will be the occurrence of an adverse event that in the opinion of the Investigator is not severe enough to warrant discontinuation but that requires the use of a prohibited medication, thereby requiring discontinuation of the participant. In such a case, the reason for discontinuation would be “need to take a prohibited medication,” not the adverse event.

All protocol-specified procedures/assessments should be performed at the EOT/early withdrawal visit (see [Table 1](#)). Participants who withdraw from the trial or have an early termination will be invited to enter the long-term safety extension (within Trial TV48125-CNS-30084) for the purpose of safety follow-up and evaluating ADA approximately 5 months (150 days [5 half-lives]) after receiving the last dose of IMP in this trial.

In the case of participants lost to follow-up, attempts to contact the participant must be made and documented in the participant’s medical records and transcribed to the CRF.

### **7.3. Lost to Follow-Up**

A participant will be considered lost to follow-up if he/she repeatedly fails to return for scheduled visits and is unable to be contacted by the investigational center.

The following actions must be taken if a participant fails to return to the investigational center for a required trial visit:

- The investigational center must attempt to contact the participant and reschedule the missed visit as soon as possible and counsel the participant on the importance of maintaining the assigned visit schedule and ascertain whether or not the participant wishes to and/or should continue in the trial.
- In cases in which the participant is deemed lost to follow-up, the Investigator or designee must make every effort to regain contact with the participant in accordance with the investigational center standard procedures (where possible, 3 telephone calls and, if necessary, a certified letter to the participant's last known mailing address or local equivalent methods). These contact attempts should be documented in the participant's medical record and transcribed to the electronic case report forms.
- Should the participant continue to be unreachable, he/she will be considered to have withdrawn from the trial with a primary reason of "lost to follow-up."

### **7.4. Trial Stopping Rules**

There are no formal rules for early termination of the trial. During the conduct of the trial, serious adverse events will be reviewed as they are reported from the investigational centers to identify safety concerns.

The trial may be terminated by the Sponsor for any reason at any time. For example, the Sponsor should terminate the trial in the event of the following:

- new toxicological or pharmacological findings or safety issues that invalidate the earlier positive benefit-risk assessment
- discontinuation of the development of the IMP

If the whole trial or arms of the trial are stopped, the participants that are terminated early will be followed according to criteria outlined in Section [7.2](#).

## 8. TRIAL ASSESSMENTS AND PROCEDURES

### 8.1. Screening/Baseline Assessments and Procedures

A signed and dated ICF will be obtained before screening procedures commence (see Section 10.3). Procedures performed at screening are listed in [Table 1](#) and Section 13.9.

Evaluations obtained as part of routine medical care and performed during the screening period may be used in place of the protocol-specific evaluations. Participants will acknowledge and agree to the possible use of this information for the trial by giving informed consent.

Participants may have individual parameters retested at the discretion of both the Investigator and the Sponsor (also see Section 5.6).

Participants who fulfil the inclusion criteria and meet none of the exclusion criteria at the screening visit may be enrolled in the trial.

### 8.2. Efficacy Assessments and Procedures

Data from any efficacy assessments performed after the specified time (see [Table 1](#)) will not be collected on the CRF; in the event, however, that such data are collected, these data will not be analyzed.

#### 8.2.1. Electronic Headache Diary

The primary efficacy endpoint (and some secondary and exploratory efficacy endpoints as well) will be derived from headache variables collected daily using an electronic headache diary device. Eligible participants and parents/caregivers will receive comprehensive training from site personnel on the use of the electronic headache diary device. Site personnel will also instruct participants and parents/caregivers on the requirement for timely and daily completion of the eDiary. Participants will complete an electronic headache diary. If the participant is unable to complete the diary themselves then a parent/caregiver will complete the diary for them.

On each day, the participant or parent/caregiver will be asked to record diary data for the previous 24-hour period. Participants and parents/caregivers may be asked about their (child's) performance at school and when doing household chores (ie, functional assessments).

Participants or parents/caregivers who report headache on the previous day will answer questions about the headache (ie, the number of hours with headache, headache severity, presence of associated symptoms, and use of acute migraine medications). Additional details regarding the questions participants or parents/guardians will answer can be found in the electronic headache diary training manual.

If a participant or parent/caregiver fails to complete the diary for the preceding day, the participant will be prompted to enter the missed day's information the next time he/she accesses the eDiary, provided no more than 48 hours have elapsed since the end of the missed day. If more than 48 hours have elapsed since completion of a diary day, the participant or parent/caregiver will not be allowed to enter diary information for that day, and it will be considered a missed day.

Rating of headache severity and headaches lasting  $\geq 2$  hours for each day will be completed in the eDiary.

If headache is reported, then headache severity will be subjectively rated by the participant or parent/caregiver on an 11-point numerical rating scale, where 0 is no pain and 10 is the most severe pain. Each headache severity rating from the 11-point numerical rating scale will be mapped to mild (1 to 3), moderate (4 to 6), or severe (7 to 10) for endpoint analyses (McCaffery and Beebe 1989). Participants or parents/caregivers will also record whether photophobia, phonophobia, nausea, and vomiting are present, and they will record any migraine medications (name of drug, number of tablets/capsules, and the dose in milligrams per tablet/capsule) taken on each day. Diary compliance of less than 75% after the start of treatment will be recorded as a protocol deviation.

### **8.2.2. Pediatric Migraine Disability Assessment**

The Pediatric Migraine Disability Assessment (PedMIDAS) questionnaire is a 6-item instrument to assess migraine-related disability in pediatric participants, which can be self-administered by the participant or administered by a caregiver. It has been validated in patients aged 4 through 18 years (Hershey et al 2001) and includes questions related to the impact of headache on school performance, disability at home (eg, inability to do chores or homework), and social/sport functioning.

### **8.2.3.**

### **8.2.4. Pediatric Quality of Life Inventory**

The Pediatric Quality of Life Inventory (PedsQL) 4.0 is a brief 23-item health-related quality of life instrument that evaluates quality of life in 4 areas of functioning: physical, emotional, social, and school functioning. The PedsQL 4.0 has 4 age ranges: toddlers (2 through 4 years), young child (5 through 7 years), child (8 through 12 years), and adolescent (13 through 18 years). This trial will use the young child, child, and adolescent formats. The PedsQL version that will be

used for the participant for the duration of the trial will be based on the age of the participant at visit 2 and will not change during the course of the trial.

The PedsQL 4.0 asks respondents to indicate how much of a problem each item has been during the past month. For the child and adolescent self-report (8 through 18 years of age) and the parent report forms, respondents use a 5-point Likert scale to rate the item severity (0=never a problem; 1=almost never a problem; 2=sometimes a problem; 3=often a problem; 4=almost always a problem). For younger children (5 through 7 years of age), a simplified 3-point Likert scale, anchored with a happy and a sad face, is used (0=not at all a problem; 2=sometimes a problem; 4=a lot of a problem) to increase further the developmental sensitivity of the measure.

The PedsQL 4.0 yields a total quality of life score and 2 summary scores: Physical Health Summary Score and Psychosocial Health Summary Score. To obtain scores, items are reverse scored, transformed to a 0 through 100 scale (0=100, 1=75, 2=50, 3=25, 4=0), and averaged; total scores near 0 indicate lower quality of life, while scores approaching 100 indicate higher quality of life.

## **8.3. Safety Assessments and Procedures**

In this trial, safety will be assessed by qualified trial personnel by evaluating reported adverse events, vital signs measurements, clinical laboratory test results, ECG findings, physical examination findings (including body weight and height measurements), suicidal ideation and behavior (as suggested by the Columbia-Suicide Severity Rating Scale [C-SSRS]), and use of concomitant medication.

### **8.3.1. Physical Examinations**

Physical examinations, including height and weight (to be obtained at the screening visit, randomization visit, and EOT only) and puberty status (at randomization and EOT only) will be performed at the time points detailed in [Table 1](#). Body mass index will be calculated at screening and randomization.

While the onset of puberty is generally associated with the onset of adolescence, a globally accepted age range for the onset of puberty and adolescence cannot be easily defined ([World Health Organization 1986](#)). Because randomization will be stratified by puberty status, the Tanner puberty staging scale ([Finegold 1992](#)) will be used to assess puberty status at that time. Puberty status will be assessed either by participants' self-report or by physical examination according to the Tanner staging card provided.

A complete physical examination will include the following organ systems: general appearance; head, eyes, ears, nose, and throat; chest and lungs; heart; abdomen; musculoskeletal; skin; lymph nodes; and neurological. Any physical examination finding that is judged by the Investigator as a potentially clinically significant change (worsening) compared with a baseline value will be considered an adverse event, recorded on the CRF, and monitored as described in [Section 8.4.5](#).

### **8.3.2. Vital Signs**

Vital signs (pulse, systolic and diastolic blood pressure (BP), temperature, and respiratory rate) will be measured at any time during the visit, as detailed in [Table 1](#). The method for measuring temperature in an individual participant must be the same at each time point.

Before pulse and BP are measured, the participant must be in a supine or semi-erect/seated position and resting for at least 5 minutes. The same position and arm should be used each time vital signs are measured for a given participant. For any abnormal vital sign finding, the measurement should be repeated as soon as possible. Any vital sign value that is judged by the Investigator as a clinically significant change (worsening) from a baseline value will be considered an adverse event, recorded on the source documentation and transcribed onto the CRF, and monitored as described in Section 8.4.5.

### **8.3.3.      *Electrocardiograms***

Twelve-lead ECGs will be conducted at any time during the visit, prior to IMP administration, as detailed in [Table 1](#). The ECGs should be performed after the participant has been supine for at least 5 minutes. The ECGs will be performed in triplicate, with at least 1 minute between recordings.

A qualified physician at a central diagnostic center will be responsible for interpreting the ECG. ECGs should be performed and transmitted according to the central ECG reading instructions provided in the ECG user manual. ECG equipment will be provided to all clinical sites.

Although the ECG interpretation will be performed centrally, the clinical evaluation remains under the Investigator's responsibility.

The ECG will be evaluated by the Investigator at the time of recording (signed and dated), and the printout should be kept in the source documentation file. When potentially clinically significant findings are detected by the Investigator, a cardiologist should be consulted for a definitive interpretation. All communications and diagnoses should be filed in the source documentation file. The Investigator's interpretation will be recorded in the CRF regardless of the central reading interpretation. Any abnormal findings assessed by the Investigator as clinically significant should be recorded in the relevant CRF modules (eg, adverse event, medical history).

Objective alerts are predefined as described in the central ECG reading manual. In these cases, the site and the Sponsor will be informed immediately.

Any unscheduled ECGs must also be submitted for central ECG reading.

Any ECG finding that is judged by the Investigator as a potentially clinically significant change (worsening) compared with a baseline value will be considered an adverse event, recorded on the source documentation and transcribed onto the CRF, and monitored as described in Section 8.4.5.

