### 3. TRIAL OBJECTIVES, ENDPOINTS, AND ESTIMANDS

#### 3.1. Primary and Secondary Trial Objectives and Endpoints

The primary and secondary trial objectives and endpoints are as follows:

Objectives	Endpoints
The primary objective of the trial is to evaluate the efficacy of test investigational medicinal product (IMP) as compared to placebo IMP for the preventive treatment of chronic migraine (CM).	The primary efficacy endpoint is the mean change from baseline (28-day baseline period) in the monthly average number of migraine days during the 12-week period after the first dose of IMP.
A secondary objective is to evaluate the safety and tolerability of test IMP in the preventive treatment of CM.	
The safety and tolerability endpoints are as follows:
 
 
• occurrence of adverse events throughout the trial, including local injection site reaction/pain
 
• abnormal standard 12-lead electrocardiogram (ECG) findings
 
• changes from baseline in vital signs (systolic and diastolic blood pressure, pulse, temperature, and respiratory rate), height, and weight measurements
 
• changes from baseline in clinical laboratory (serum chemistry, hematology, coagulation, and urinalysis) test results
 
• abnormal physical examination findings
 
• suicidal ideation and behavior as suggested by the Columbia-Suicide Severity Rating Scale (C-SSRS)
 

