### **9.4. Analysis of Exploratory Objective(s)**

### **9.5. Safety Analyses**

Safety analyses will be performed on the safety analysis set (Section 9.1.1).

Safety assessments and time points are provided in [Table 1](#).

All adverse events will be coded using the Medical Dictionary for Regulatory Activities. Each participant will be counted only once in each preferred term or system organ class category for the analyses of safety. Summaries will be presented for all adverse events (overall and by severity), adverse events determined by the Investigator to be related to test IMP (and/or PFS) (ie, reasonable possibility) (defined as related or with missing relationship) (overall and by severity), serious adverse events, serious adverse device effects, protocol-defined adverse events of special interest, adverse events, and adverse device effects causing withdrawal from the trial. Summaries will be presented by treatment group and for all participants. Participant listings of serious adverse events, serious adverse device effects, adverse events, and adverse device effects leading to withdrawal will be presented.

Changes in laboratory, ECG, and vital signs measurements data will be summarized descriptively. All values will be compared with predefined criteria to identify potentially clinically significant values or changes, and such values will be listed.

Suicidal ideation and behavior will be measured using the C-SSRS. Data for participants with positive findings will be listed.

The use of concomitant medications will be summarized by therapeutic class using descriptive statistics. Concomitant medications will include all medications taken while the participant is treated with IMP.

For continuous variables, descriptive statistics (n, mean, SD, median, minimum, and maximum) will be provided for actual values and changes from baseline to each time point. For categorical variables, participant counts and percentages will be provided. Descriptive summaries of serious adverse events, participant withdrawals due to adverse events, and potentially clinically significant abnormal values (clinical laboratory or vital signs) based on predefined criteria will be provided as well.

If any participant dies during the trial, a listing of deaths will be provided, and all relevant information will be discussed in the participant narrative included in the CSR.

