5.5. Prior Therapy and Medication

Any prior therapy, medication, or procedure a participant has had before IMP administration will be recorded on the CRF. Trade name or INN, indication, and dosage will be recorded. The

sponsor will encode all therapy and medication according to the World Health Organization (WHO) drug dictionary (WHODrug).

The incidence of prior therapies and medications will be summarized using descriptive statistics by therapeutic class and PT. Participants are counted only once in each therapeutic class category, and only once in each PT category. Prior therapies and medications will include all medications taken and therapies administered before the 1st day of IMP administration.

The subset of prior medications will be summarized for the following categories.

- Medication from Appendix C for migraine/headache
- Medication from Appendix C for other reason than Migraine/Headache
- Migraine/headache prevention medication not from Appendix C
- NSAIDs for migraine/headache
- NSAIDs for other reason than migraine/headache
- Triptan for migraine/headache
- Triptan for other reason than migraine/headache
- Ergot for migraine/headache
- Ergot for other reason than migraine/headache
- Medication used for symptoms during migraine attack other than pain
- Other

5.6. *Electrocardiography*

Electrocardiogram findings by Investigator (normal, abnormal not clinically significant and abnormal clinically significant) and by Cardiologist (normal, abnormal) overall and at last visit will be summarized.

5.7. *Physical Examinations*

Physical examinations results will be listed. Participants with at least 1 abnormal finding (overall) and abnormal findings for each category will be summarized.

5.8. *Childbearing Potential and Methods of Contraception*

All participants must be of non-childbearing potential or be using highly effective contraception as defined in the protocol. Information related to childbearing potential will be collected and listed.

Methods of contraception will be collected and this data will be listed.

5.9. *Trial Protocol Violations*

Protocol deviations (PD) will be collected and reviewed by the trial team prior to database lock and will be provided in a data listing. Participants with at least 1 important protocol deviation will be summarized for each category using descriptive statistics.

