8.9. Electrocardiography

ECGs will be performed in triplicate, with approximately 1 minute between recordings. The average of the recorded measurements will be calculated for each visit.

Any ECG finding that is judged by the Investigator as a potentially clinically significant change (worsening) compared with the baseline value will be considered an adverse event.

For ECG variables, the mean of recorded results from last three measurements at a visit will be calculated. The mean results and mean changes from baseline to each visit in the treatment period and Last Assessment (see Section 4.4) will be summarized using descriptive statistics. Baseline is determined based on the last set of observed data before the administration of the 1st dose of the IMP.

For ECG findings, the worst value of recorded from last three findings at a visit will be used for analysis. Baseline ECG findings and shifts (normal, abnormal not clinically significant, and abnormal clinically significant) from baseline to each visit in the treatment period, Overall (worst value for a participant), and the Last Assessment (worst value of recorded findings from the last visit) will be summarized using participant counts.

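### The ECG check against predefined criteria in Protocol 9.5 has no counterpart in the SAP, and the omission is not declared

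*Protocol*

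**What the plan says.** Protocol 3.1 lists "abnormal standard 12-lead electrocardiogram (ECG) findings" among the safety endpoints. Protocol 9.5 opens its paragraph on measurements with "Changes in laboratory, ECG, and vital signs measurements data will be summarized descriptively" and continues directly with "All values will be compared with predefined criteria to identify potentially clinically significant values or changes, and such values will be listed". A later sentence in 9.5 promises summaries of "potentially clinically significant abnormal values (clinical laboratory or vital signs) based on predefined criteria will be provided as well"; ECG is not named there.

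On reading, Protocol 8.3.3 says "A qualified physician at a central diagnostic center will be responsible for interpreting the ECG" and "Objective alerts are predefined as described in the central ECG reading manual". Alerts go at once to the site and the Sponsor, and unscheduled tracings are also sent for central reading. The CRF holds the Investigator's interpretation whatever the central result.

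SAP 8.9 averages the last three measurements at a visit. "The mean results and mean changes from baseline to each visit in the treatment period and Last Assessment" are then summarized with descriptive statistics, which SAP 8.1 defines to include SD, minimum and maximum. For findings, 8.9 takes the worst of the last three and tabulates shifts across normal, abnormal not clinically significant and abnormal clinically significant. The shifts run to each visit, to the participant's overall worst and to the last assessment. No reader is named.

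SAP 5.6, under Trial Population, refers to "Electrocardiogram findings by Investigator (normal, abnormal not clinically significant and abnormal clinically significant) and by Cardiologist (normal, abnormal"); the sentence ends by giving the time frame as overall and the last visit.

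**The concern.** The protocol sets up one outlier check for three kinds of safety data, and the SAP completes it for two. The SAP states that it prevails where the documents differ, so a reader who follows the SAP will produce no ECG check at all. Nothing in Section 15, the SAP's list of changes to protocol analyses, says that this was intended.

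ECG safety signals usually show as a few individuals with large changes, and averages are poor at showing those. The shift table depends on how investigators at about 85 centers classify tracings. The central alerts are the one set of fixed criteria that the documents mention, and no planned analysis uses them. At stake is whether the report on a stated safety endpoint can say how many participants in each group crossed a fixed ECG threshold, and who they were. No efficacy conclusion is affected.

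**Working it through.** **1. Promise against delivery**

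| Data | Comparison and listing in Protocol 9.5 | Criteria in SAP | Count in SAP | Listing of flagged values in SAP |
|---|---|---|---|---|
| Laboratory | yes | Table 4 | yes (8.6) | yes (8.6) |
| Vital signs | yes | Table 5 | yes (8.8) | yes (8.8) |
| ECG | yes, named in the preceding sentence | none | none | none |

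SAP 4.1 says that summaries of potentially clinically significant values include every postbaseline value, unscheduled ones too. ECG has no such summary, so that rule never reaches it. SAP 15 lists two dropped subgroup analyses and one excluded site, and nothing on ECG.

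**2. What SAP 8.9 would show for an outlying tracing**

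- *Investigator rates it abnormal.* It is counted in the shift table, and the worst-of-three rule keeps it. If judged a potentially clinically significant worsening, it becomes an adverse event and is listed by participant.
- *Numeric outlier in all three recordings, rated normal.* It enters the mean and SD and may appear as the maximum. It is not counted, and no participant is identified.
- *Numeric outlier in one of three recordings, rated normal.* It is first averaged with the other two, so even the maximum shows a reduced value.
- *Outlier in an earlier set, with the triplicate repeated at the same visit.* Only the last three are used, so the earlier set leaves both the average and the worst-finding rule.

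**3. Size of the dilution (illustration)**

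The plan states no ECG figure to reproduce. The only documented input is group size: 266/(1 − 0.04) = 277.1, giving the stated 278 randomized, or 139 per group. SAP 8.1 presents safety as 225 mg, 120 mg and placebo, so only the placebo column approaches 139. The sizes of the two fremanezumab columns are not given; being smaller, they dilute less.

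The change d in one participant is assumed, with no change in the others, and with the other two recordings unchanged where only one is affected. Shift in column mean = d/n. If only one recording is affected, the participant's value is d/3 and the shift is (d/3)/n. With n = 139:

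| d (units, assumed) | Mean shift, all three recordings | Participant's averaged value, one of three | Mean shift, one of three |
|---|---|---|---|
| 30 | 0.22 | 10 | 0.07 |
| 60 | 0.43 | 20 | 0.14 |
| 120 | 0.86 | 40 | 0.29 |

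The mean does not reveal such a participant. With all three recordings affected, the maximum would show d for the most extreme person only. With one affected, it would show at most a third of d for that person, who may not be the column's extreme.

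**4. Whose reading the shifts use**

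The three levels in 8.9 match the scale that SAP 5.6 gives to the Investigator; the Cardiologist's scale there has two levels. The Investigator is therefore the natural inference, but 8.9 does not say so. It also gives no source for the numeric ECG variables, which may be central measurements.

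**The case against.** The strongest reply is that individual outliers are better covered than the missing table suggests. SAP 8.1 reports minimum, maximum and SD for values and changes. SAP 8.9 keeps each participant's worst finding. Alerts reach the site and Sponsor immediately, and investigator-judged worsening becomes a listed adverse event. All of this stands, and it rules out a reading that a reader might infer: that an ECG outlier can disappear altogether from the results. The documents do not support that. A large change in all three recordings would move the maximum, and any tracing the Investigator calls abnormal is counted by treatment group. None of these routes, however, supplies the comparison with fixed criteria.

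A reader might also infer that the central read is left out of the treatment-period analysis. That is not established either. SAP 5.6 summarizes a Cardiologist's reading over a time frame that could be the whole trial, although its placement under Trial Population, and the ECG item in Protocol 9.1.5.2, point to a baseline display. Nor do the documents say that this Cardiologist is the central reader, since Protocol 8.3.3 also mentions a cardiologist consulted by the Investigator.

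Next, the summary sentence in Protocol 9.5 names only laboratory and vital signs. That stands: for ECG the protocol promises comparison and a listing, and a count by treatment group goes one step further, in line with what the SAP does for the other two.

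Finally, the manual's thresholds are not in the documents and may have been set for immediate notification rather than analysis. That also stands. As for Section 15, the SAP says differences will be explained in the CSR, so its silence can still be remedied there.

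**Conclusion.** The point holds as an undeclared omission. The ECG part of the check in Protocol 9.5 was not carried into the SAP, and what replaces it neither counts nor identifies a numeric outlier that is rated normal locally or confined to one recording. Its practical weight is moderate: it limits the reporting of one safety endpoint, with partial cover from the maximum, the worst-finding shifts and adverse event reporting.

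This rests on taking the sentence about all values in 9.5 to cover the three data types named just before it, which is the plain reading. The dilution figures rest on assumed changes of 30 to 120 units and a column of 139; they illustrate the mechanism and do not predict any result. Whether a central reading is summarized for the treatment period remains unclear from SAP 5.6.

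**What to change.** In SAP 8.9, add ECG criteria set by the sponsor, for example those in the central ECG reading manual if they suit analysis. List the participants who meet any criterion on any postbaseline tracing, including unscheduled and repeated ones, and count them by treatment group. Name the reader behind the 8.9 shifts and the source of the numeric variables. If the central normal/abnormal interpretation is in the database, show it for treatment visits beside the Investigator's categories. State in 5.6 which visits are covered and who the Cardiologist is.

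The note to file at the end of the SAP says the analysis has been conducted. The output should therefore be reported as an additional analysis and disclosed as such in the CSR, which Protocol 9 provides for. If the sponsor decides against it, the CSR should state that the ECG comparison and listing were not done, and why.

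The cost is one table, one listing and some wording, with no new data collection provided the central results are held in usable form. The downside is that some isolated threshold crossings will need comment.
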